To determine the sample size for a test of non-inferiority for unventilated filter cigarettes compared to ventilated filter cigarettes (control group), we used pilot data from our original ventilated/unventilated study 1 ([name], personal communication). For the purposes of sample size considerations, we will focus on total NNAL as one of the primary outcomes. Seventy subjects had a baseline NNAL value while smoking their usual brand and 19 and 16 subjects had an end of study NNAL value for the ventilated and unventilated groups, respectively. The endpoint of interest is the change in NNAL from baseline. To normalize the distribution of NNAL, the calculations were performed in the log scale. The non-inferiority margin (NIM) was set at a 15% change between groups. This criterion was chosen because it is close to, but not greater than the upper limit of the 95% confidence interval (CI) for the geometric mean of the change in NNAL. Therefore, 73 subjects per group will achieve 80% power to detect non-inferiority for the mean change in NNAL using a one-sided, two sample t-test with a significance level of 0.05. Furthermore, with these sample sizes, a one-sided, two-sample t-test for the mean difference in cigarettes per day (CPD) from baseline will have 90% power to determine non-inferiority with a significance level of 0.05 if the NIM is 2 cigarettes. A mean difference between ventilation groups of less than 2 cigarettes is considered to be in the range of equivalence. To accommodate a 10% loss-to-follow-up rate, we plan to enroll 81 subjects per group for a total of 162.

Study Populations

Intent-to-treat

The first analysis of all primary and secondary endpoints will adhere to the intent-to-treat principle. Under this principle, all subjects randomized to one of the two study arms will be included in the analysis in the group to which they were randomized regardless of protocol violations and compliance to treatment assignment.

Per-Protocol

A second per-protocol analysis will include only participants who complete the 6 week visit without protocol violations or non-compliance.

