Every effort will be made to limit the amount of missing data in this trial. Study participants will be incentivized to attend study sessions. That said, some level of missing data is inevitable in a study of this kind. We will compare subjects who do and do not complete the study sessions in order to identify baseline covariates associated with study completion.

Our primary approach to handling missing data will be a sensitivity analysis using multiple imputation with the Markov Chain Monte Carlo (MCMC) method³⁵ carried out in PROC MI in SAS, where missing values are imputed using regression models developed from baseline covariates. Values can be imputed for both continuous and categorical variables. If the ventilation groups are associated with missing data, we will conduct multiple imputation for each ventilation group separately. Following imputation, standard statistical methods can be applied. A final single

assessment of ventilation group difference will be obtained from combining the results across the imputed datasets using PROC MIANALYZE in SAS.

Interim Analyses

No interim analysis is planned.

11 Supporting Documentation and Operational Considerations

Informed Consent Procedure and Documentation

Potential subjects will be told the nature of the research over the phone during screening and then at a virtual orientation meeting where the study is described in detail. All potential study participants will be provided a copy of the IRB-approved consent form to review prior to signing. They will be told they may discontinue participation at any time and will not be discriminated against if they choose to do so. Subjects will be told their participation in the project will be strictly confidential, that any identifying information will be available to the project investigators or institutional or federal regulatory groups only, and that no identifying information concerning the data and results will be made known. The investigator or designee will explain all aspects of the study in lay language and answer all questions regarding the study. Subjects will be required to demonstrate an understanding of the study purpose and procedures prior to signing the consent form. If the participant decides to participate in the study, he/she will be asked to sign and date the consent document and will receive a copy for their records. Consent form must be signed before the research is started.

Confidentiality of Data

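### All planned missing-data handling assumes missing at random, so nothing in the plan tests whether dropout driven by rising intake in the unventilated arm would overturn non-inferiority

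*Combined protocol and SAP*

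**What the plan says.** Section 10.2, under Missing Data, states: "Our primary approach to handling missing data will be a sensitivity analysis using multiple imputation". It describes a Markov Chain Monte Carlo imputation "where missing values are imputed using regression models developed from baseline covariates". Imputation is done separately by arm only if arm turns out to be associated with missingness. Otherwise the text does not say that arm is in the model. Completers and non-completers are also to be compared on baseline covariates.

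The primary analysis in the same section is an unadjusted non-inferiority t-test on the change from visit 00 to Week 6. No rule is given for a participant without a Week 6 value, although the intent-to-treat set in Section 10.1 is everyone randomised. The supplements are a regression on the visit 00 value, site and unbalanced characteristics, and a mixed model over all visits from 00. The per-protocol set is restricted to participants who complete Week 6. No delta-adjusted, tipping-point, reference-based or other not-at-random analysis appears.

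On loss, Section 10.1 says: "To accommodate a 10% loss-to-follow-up rate, we plan to enroll 81 subjects per group for a total of 162".

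**The concern.** The imputation treats a missing participant as resembling observed participants with the same baseline covariates. In this trial the damaging case is different: someone in the unventilated arm whose NNAL or cigarettes per day (CPD) rose after randomisation, and who left for that reason. Losing such people moves the estimate towards the conclusion the trial hopes to reach.

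The protocol makes this plausible. Section 7 says guidelines exist for terminating participants so as to avoid a marked rise in smoking, which ties withdrawal to a primary endpoint. It also foresees headache, nausea, throat irritation or cough with the unventilated cigarettes. Section 10.1 reports 70 pilot participants with a baseline NNAL but only 19 + 16 = 35 with an end-of-study value. The reason is not stated, so this is only a caution about the 10% allowance.

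If the t-test and the imputation agreed, the report could present that agreement as robustness, although neither analysis addresses this case.

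**Working it through.** **Inputs from Section 10.1.** The test is specified as "using a one-sided, two sample t-test with a significance level of 0.05"; "73 subjects per group will achieve 80% power to detect non-inferiority for the mean change in NNAL"; "The non-inferiority margin (NIM) was set at a 15% change between groups", taken here as log 1.15 = 0.1398; for CPD, "90% power to determine non-inferiority with a significance level of 0.05 if the NIM is 2 cigarettes". No standard deviation is given.

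**The plan's own figure.** 73 × 1.10 = 80.3, rounded up to 81 per group; 73/0.90 = 81.1. Conversely 81 × 0.90 = 72.9. The stated 81 is reproduced.

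**SD, back-solved with a true difference of 0 (an assumption).** √(2/73) = 0.1655.
- Log NNAL: 0.1398 / [(1.645 + 0.842) × 0.1655] = 0.340; the exact t calculation gives 0.338, used below.
- CPD: 2 / [(1.645 + 1.282) × 0.1655] = 4.13.

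**Completers' bound.** SE = 0.338 × 0.1655 = 0.0559. With t = 1.656 on 144 df, the half-width is 0.0926. At an observed ratio of 1.00 the upper bound is exp(0.0926) = 1.097.

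**NNAL tipping value.** If a fraction p of the unventilated arm is missing and their log NNAL lies δ above the missing-at-random value, the all-randomised difference is the observed difference plus pδ. The verdict reverses at δ = (0.1398 − log observed ratio − 0.0926)/p.

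| Missing p | Observed 1.00: δ | Excess | Observed 1.03: δ | Excess |
|---|---|---|---|---|
| 10% | 0.471 | 60% | 0.176 | 19% |
| 15% | 0.314 | 37% | 0.117 | 12% |
| 20% | 0.236 | 27% | 0.088 | 9% |

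The 73-per-arm SE is kept throughout. Reducing the unventilated arm at 15% and 20% missing lowers the excess to about 36% and 25% (ratio 1.00) and about 11% and 8% (ratio 1.03).

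**CPD tipping value, observed difference 0.** SE = 4.13 × 0.1655 = 0.684, so (2 − 1.656 × 0.684)/p = 0.868/p, or 8.7, 5.8 and 4.3 cigarettes per day at 10%, 15% and 20% missing.

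**False non-inferiority when the true all-randomised ratio is exactly 1.15.** The observed log difference is too low by pδ, so the error is approximately Φ(pδ/0.0559 − 1.656). Simulations used 81 per arm, 10% missing on ventilated, an assumed between-subject SD of 0.8, 20 imputations by arm and 1,500 trials per setting. The range over two runs is shown.

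| Missing, excess in the missing | pδ | Formula | Simulated t-test | Simulated imputation |
|---|---|---|---|---|
| 10%, 49% | 0.10 × 0.399 = 0.040 | 17% | 17% | 16–17% |
| 15%, 35% | 0.15 × 0.300 = 0.045 | 20% | 18–21% | 18–21% |
| 20%, 28% | 0.20 × 0.247 = 0.049 | 22% | 19–22% | 19–21% |

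Monte Carlo error is about √(0.2 × 0.8/1500) = 1 percentage point. The two analyses gave the same verdict in 97 to 99% of trials. A harsher assumed model, in which larger NNAL rises made dropout more likely, gave 31% (t-test) against 27% (imputation) at about 13% missing, and 67% against 60% at about 33%.

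**Arm left out of the imputation model.** With a true log difference of 0.140 and dropout completely at random, the mean estimate fell to about 0.128 at 10% missing and 0.096 at 30%. False non-inferiority rose to 7% and 11%.

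**The case against.** A reader might infer that the imputation makes the same assumption as the completers' t-test and must reproduce its answer. The documents do not support that. The unadjusted t-test on completers needs dropout unrelated to change within arm, whereas the imputation also allows dropout to depend on baseline covariates. It can therefore differ from the t-test and improve on it. In simulations where dropout depended on baseline NNAL in opposite directions by arm, the t-test was off by 0.02 to 0.06 log units and imputation removed the error. With a true difference of 0, verdicts agreed in only 88% of trials at about 13% missing and 71% at about 33%. The planned imputation is thus a partial sensitivity analysis. Near-identity is to be expected only against a complete-case regression on the same baseline covariates, which is a supplement here.

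Some of the needed information is also collected. Urine is taken at Week 3 and at early termination (Sections 5.7 and 5.10), Week 3 NNAL can enter the mixed model, and daily texts with Timeline Follow-back recover missing CPD. A rise before leaving is thus partly observed. This stands, but the imputation as written does not use those values, and the mixed model still assumes missing at random.

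Finally, at the planned 10% loss and an observed ratio of 1.00 the excess needed is about 60%. That also stands and limits the size of the concern.

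**Conclusion.** The gap is real: no planned analysis departs from missing at random, and the imputation model need not include arm. Where dropout follows a post-randomisation rise in intake, the t-test and the imputation by arm err together, at about 16 to 22% against 5% nominal in the scenarios assumed. It would be wrong to infer that non-inferiority is fragile at the planned loss. Fragility arises mainly with higher loss or a result near the margin, as the fall from a 60% to a 9% tipping excess shows.

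These sizes rest on SDs back-solved from 73 per group, on dropout excesses and loss above 10% that the documents do not give, and on reading the t-test as a completers' analysis, which the plan does not state.

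**What to change.** In Section 10.2, Missing Data:

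1. Always impute by arm, or include arm in the model, and add the Week 3 and early-termination values as predictors. Keep this as the δ = 0 analysis.
2. Add a delta-adjusted imputation that shifts imputed Week 6 values in the unventilated arm upward: log NNAL from 0 to log 1.15 and on until the verdict changes; CPD from 0 to 2.0 cigarettes and on until it changes.
3. Report the result with δ at the margin, and the tipping value, beside the primary result for each endpoint. Leave the primary decision rule unchanged.

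The cost is a paragraph of SAP text and a few lines of code between PROC MI and PROC MIANALYZE; no new data are needed. The downside is a little more analysis, and a report that may show the verdict to be fragile.

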10.2 Statistical analysis plan

The primary objective of the statistical analysis is to compare the effects of cigarette ventilation between two study groups: ventilated filter cigarettes and unventilated filter cigarettes. All statistical analyses will be performed using SAS version 9.4 (SAS Institute Inc., Cary NC) and a p-value less than 0.05 will be considered significant.

Describing the Study Population

Descriptive statistics will be performed for data collected on demographic characteristics, subjective measures and biomarkers at different phases and visits. Baseline data will be compared between the two ventilation groups with the two-sample t-test or the non-parametric Wilcoxon rank sum test for continuous or ordinal variables and chi-square tests for categorical variables. Biomarker data may be log transformed if necessary.

Primary Endpoint Analysis

The primary endpoints are (1) the total NNAL at the 6-week visit adjusted for NNAL at end of Phase 2 (visit 00); and (2) the mean CPD based on 7 days ITR data before week 6 visit adjusted for the mean CPD during Phase 2 (visit 00). The analysis of these two endpoints will evaluate non-inferiority of the unventilated group compared to the ventilated group.

Primary Analysis

The primary analysis will be a one-sided, two-sample t-test for non-inferiority. The null hypothesis for total NNAL (analyzed in the log scale) is that the increase from end of Phase 2 (visit 00) is 15% greater in the unventilated group compared to the ventilated group. The NNAL alternative hypothesis is that the increase from baseline (visit 00) is no higher than 15% in unventilated over ventilated groups. If the null hypothesis is rejected in favor of the alternative hypothesis, we will conclude that the unventilated filters are no more harmful in terms of NNAL exposure than the ventilated filter and may actually be less harmful. Similarly for the CPD, the non-inferiority t-test will have a null hypothesis that the 6 week mean increase in CPD from end of Phase 2 (visit 00) for the unventilated group is greater than 2.0 cigarettes compared to the ventilated group. The alternative hypothesis is that the CPD increase in the unventilated group is no more than a mean of 2.0 cigarettes verses the CPD increase in the ventilated group and the unventilated group may even smoke fewer cigarettes.

Secondary Analysis

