The above methods will be supplemented with multiple linear regression analysis to include the baseline (visit 00) value for NNAL or CPD and the stratification variable (site), plus any other subject specific characteristics which might not be balanced between the study groups (p-value<0.2).

Finally, NNAL and CPD will be analyzed for all visits, starting at visit 00, using a linear mixed effects model (SAS PROC MIXED). The fixed effects are ventilation group indicator, plus other potential predictors. To model the variation within subjects, several candidate variance-covariance structures will be compared using both graphical and information criteria. Variance parameters will be estimated using restricted maximum likelihood method with the Satterthwaite approximation. This analysis will provide useful information about the change in toxicant exposure and the change in the number of cigarettes smoked per day over time.

Both linear regression models and repeated measures analysis can be modified for the equivalence and non-inferiority testing situations.³⁴

Secondary Endpoint Analysis

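### Study arm should always be in the imputation model; tying it to differential dropout shrinks the arm difference and tilts the check modestly toward non-inferiority

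*Combined protocol and SAP*

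**What the plan says.** Section 10.2, Missing Data, specifies multiple imputation by MCMC in PROC MI, in which "missing values are imputed using regression models developed from baseline covariates". Arm appears only in a conditional: "If the ventilation groups are associated with missing data, we will conduct multiple imputation for each ventilation group separately". No threshold is given for that association. The output is a single "assessment of ventilation group difference will be obtained from combining the results across the imputed datasets using PROC MIANALYZE in SAS".

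The role of the imputation is described as follows: "Our primary approach to handling missing data will be a sensitivity analysis using multiple imputation". Under Primary Analysis, "The primary analysis will be a one-sided, two-sample t-test for non-inferiority", with margins of 15% for NNAL and 2.0 cigarettes for CPD. That subsection does not say whether the t-test uses observed or imputed Week 6 values. The intent-to-treat paragraph in section 10.1 keeps every randomised subject in the analysis. The sample-size paragraph there allows for 10% loss and enrols 81 per group.

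Elsewhere in section 10.2 the authors name the group indicator when they want it in a model: it is a fixed effect in the mixed model and a term in the FTND regression.

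**The concern.** Whether arm predicts missingness is not what decides if arm belongs in the imputation model. It belongs there because the imputed data are used to estimate the arm effect on the outcome. The rule as written leaves arm out when dropout is similar in the two groups, and that is a case where leaving it out still biases the difference toward zero.

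In a superiority trial this would be conservative. Here the claim is non-inferiority, so shrinkage toward zero favours the claim whenever unventilated cigarettes truly raise exposure or consumption. A check on the primary result would then lean the same way as the result it is meant to probe. If the intent-to-treat t-test is itself run on imputed data, which the text does not rule out, the bias enters the primary result.

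**Working it through.** **Inputs from section 10.1.** 73 evaluable per group; 80% power for NNAL at a 15% margin and 90% for CPD at 2 cigarettes; one-sided 0.05; 10% loss; 81 enrolled per group. Inflating 73 by 10% gives 73 × 1.10 = 80.3, so 81, which reproduces the plan's figure. (Dividing by 0.9 gives 81.1, so 82.)

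**SD of change (not stated, so back-solved with true difference zero).** SD ≈ margin / [(z₀.₉₅ + z_power) × √(2/73)].
- NNAL: ln(1.15) = 0.1398; 0.1398 / (2.487 × 0.1655) ≈ 0.340. The exact noncentral-t value is 0.338.
- CPD: 2 / (2.927 × 0.1655) ≈ 4.13. The exact value is 4.11.

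**Shrinkage.** Let a fraction m be missing in each arm. With arm omitted, each arm's completed mean is (1 − m) × its own mean + m × a common mean, because randomisation balances the visit 00 predictors. The difference becomes (1 − m)δ, and the SD does not enter. At m = 0.10:
- NNAL: 0.9 × 0.1398 = 0.1258, and exp(0.1258) = 1.134.
- CPD: 0.9 × 2.0 = 1.8.

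**Error at the margin.** Simulation assumptions: 81 per arm, 10% missing completely at random, correlation between visits 0.5 to 0.9, 20 Bayesian-regression imputations, t-test on change, Rubin's rules, 8,000 trials per setting (Monte Carlo SE about 0.25 points). The Week 3 row also assumes the same arm effect at Week 3 and that half of those missing Week 6 have a Week 3 value.

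| Method | NNAL estimate (true 1.15) | NNAL non-inferiority declared | CPD estimate (true 2.0) | CPD non-inferiority declared |
|---|---|---|---|---|
| Observed values | – | 4.8-4.9% | – | 4.9% |
| Imputed, visit 00, no arm | 1.134 | 6.1-6.4% | 1.80 | 6.8-7.5% |
| Imputed, visit 00 + Week 3, no arm | 1.137-1.138 | 5.5-6.1% | 1.83-1.85 | 6.0-6.7% |
| Imputed by arm, visit 00 | – | 4.6-4.8% | – | 4.8-5.0% |

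A hand check uses a separate NNAL simulation with a generic covariate. With arm omitted, the estimate averaged 0.1251, its true SD was 0.0504, and Rubin's SE was 0.0557. A trial passes if the estimate is below 0.1398 − 1.656 × 0.0557 = 0.0476. Then (0.0476 − 0.1251)/0.0504 = −1.54, or about 6.2%; the simulated rate was 6.1%. Rubin's SE exceeds the true SD, and this offsets part of the bias. Further runs under other settings gave 5.5-6.6% for NNAL and 6.4-7.4% for CPD.

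**Other scenarios, arm omitted.**
- True NNAL ratio 1.00 (correlation 0.7): estimate 1.000; non-inferiority declared in 82.4%, against 80.3% by arm and 80.1% observed.
- True ratio 0.90: estimate 0.91.
- 5% missing: NNAL error 5.4-5.6%.
- 20% and 30% missing: 8.1% and 10.9% for NNAL, 10.6% and 14.1% for CPD.

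**The trigger.** The plan has two cut-offs it might borrow: "a p-value less than 0.05 will be considered significant" in general, and 0.2 for choosing covariates ("plus any other subject specific characteristics which might not be balanced between the study groups (p-value<0.2"). For a chi-square test with 81 per arm, the probability that imputation by arm is triggered is:

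| Dropout, arm vs arm | at 0.05 | at 0.2 |
|---|---|---|
| 10% vs 10% | 4.9% | 21.6% |
| 7% vs 13% | 24.3% | 52.3% |
| 5% vs 15% | 57.9% | 82.9% |

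With equal 10% dropout, arm is therefore left out in 95% or 78% of trials. The error of the rule as a whole is (1 − trigger) × no-arm error + trigger × by-arm error. For NNAL the extremes are 0.784 × 6.06 + 0.216 × 4.76 = 5.8% and 0.951 × 6.43 + 0.049 × 4.64 = 6.3%. For CPD the same sum gives 6.3-7.3%.

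**The case against.** The strongest reply is that the plan calls the imputation a sensitivity analysis. The observed-data t-test then keeps about 5% error under missing completely at random, and a check run after it cannot add false claims. Requiring both to pass lowers the rate, for example 4.76% × (1 − 0.053) = 4.5%. This stands. The 6-7% figures are error rates of the imputed analysis taken alone, and they become the trial's error only if the t-test is run on imputed data.

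Second, the text never expressly excludes arm, so the defect rests on a reading. That is true. But arm is named only inside the conditional, and is named outright in the models meant to contain it. On the more generous reading the section still needs a sentence saying so.

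Third, the missing fraction may be below 10%. Early-termination visits collect urine (section 5.10), although the plan does not say how those values are used. Missed daily texts are recovered by follow-back (section 5.4), so CPD is missing mainly for subjects who are lost. Both points limit the size of the effect.

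Fourth, the mixed model carries group, and the plan notes that "Both linear regression models and repeated measures analysis can be modified for the equivalence and non-inferiority testing situations". This gives some protection, but it is worded as a possibility and not a commitment.

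Finally, it can be asked how often the check overturns a pass on observed data at a true NNAL ratio of 1.15. Imputation without arm does so in 2-5% of such passes and imputation by arm in 8-18%. These are shares of the roughly 4.8% of trials that pass. Because the simulated data are missing completely at random, part of the contrast is imputation noise. At a true ratio of 1.00 the figures are 0.9% and 1.9%. I give them little weight: neither version is a strong check at 10% loss.

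**Conclusion.** The concern holds. The condition is the wrong one, and on its natural reading the imputed arm difference is shrunk by about the missing fraction, whatever the SD. At the planned 10% loss the effect is modest: false non-inferiority on the imputed data rises by roughly 1 to 2.5 percentage points at the margin, and by less at lower loss. The error rates rest on back-solved SDs, equal dropout and data missing completely at random. There is no bias if the arms are equal, and a true reduction is pulled toward no difference. The primary result is affected only if the t-test uses imputed values, which the plan leaves open. The change should be made because the rule is wrong as written and costs almost nothing to correct.

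**What to change.** Delete the conditional. Suggested text: *Missing Week 6 values will be imputed separately by randomised group, using the visit 00 value, site and the Week 3 value.* Always including arm as a predictor in one pooled model would also do. Adding Week 3 alone would not, since it repairs only part of the shrinkage.

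In the same edit, state that the primary t-test uses observed Week 6 values and the imputation is the sensitivity analysis, or the reverse.

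Optionally, if a stronger check is wanted, add a run that worsens the imputed unventilated values by a stated amount, because any missing-at-random imputation is a limited check at 10% loss.

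The cost is two or three SAP sentences and a few lines of PROC MI code (a BY statement for arm). Section 5.7 already schedules Week 3 samples, so no new data are needed.
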